5 STATISTICAL ANALYSIS

Analysis 1 and 2 will directly compare BEA and perometer assessment at a given time point (6 and 18 months). The reported concordance/correlation in small series is 0.93¹³⁴¹. Thus, even if a sleeve has been applied in patients before 6 months' measurements and the arm circumference has been reduced, the reduction in fluid in the arm should have reduced both the perometer and BEA scores concomitantly.

Sample Size Calculation

We estimate 1100 women are needed for screening by perometer to recruit 270 women to the PLACE trial and this sample size of 1100 (derived from having approached 1500 women to take part in the study) allows us to assess equivalence for sensitivity and specificity for BEA compared to perometer measurement with tight confidence intervals. Previous reported correlation between the techniques is very high¹¹⁵, and this sample size allows us to have a 95% Confidence Interval (CI) around our sensitivity and specificity estimates such that they are $\pm 5\%$ or less. Thus if perometer and BEA are equivalent in sensitivity and specificity to within 5% of each other, we would expect that the BEA would become the preferred option as it would be mobile, non-invasive and simpler to use in any outpatient setting compared to a fixed, large instrument, such as the perometer. There will be less patients with lymphoedema at 6 months but nonetheless if BEA sensitivity is 95% of the perometer sensitivity, we can demonstrate this with a 95% CI of 91.42% to 97.49%. If the BEA sensitivity rate was as low as 90%, we would have a 95% CI of 85.12% to 93.49%. All subsequent analyses will use sample sizes based on larger numbers as there will be more lymphoedema events at 18 months and again at 36 months but their confidence intervals are within $\pm 5\%$. We have used the exact method for calculating confidence intervals for a binomial proportion (Documenta Geigy Scientific tables page 185 equation 769); the actual calculation was done using the www.measuringusability.com/wald.htm website calculator.

The sample will allow us to measure accurately, inter- and intra-technique variability at different time points.

Analyses 1 to 3 will assess whether BEA can be used instead of perometer in defining lymphoedema status. The second group of analyses is to look for any variables collected at operation or in the first 6 months post operation that singly or in combination can be used to predict lymphoedema status at or beyond 18 months.

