Analysis 1

Sensitivity and specificity analysis of the BEA assessment (lymphoedema or not) against the 'gold standard' perometer assessment (lymphoedema or not) using data available by 6 months.

Analysis 2

Analysis of the sensitivity and specificity of the 18 month BEA assessment status (lymphoedema or not) against the 'gold standard' 18 month perometer assessment status (lymphoedema or not) using all data available at 18 months.

Analysis 3

Assessment of the relationship between perometer measurement and BEA measurement.

Analysis 4

Cox regression multivariate analysis of the time to Lymphoedema (as defined by perometer) to find out which combination of variables gives the best prediction of this complication.

Analysis details:

Analysis 1: Sensitivity and specificity analysis of the BEA assessment (lymphoedema or not) against the 'gold standard' perometer assessment (lymphoedema or not) using data available by 6 months. Can BEA be used instead of perometer in predicting lymphoedema status?

All cases with a 6 month BEA and perometer measurement will be used. This is acceptable even if some cases are treated as what we are asking is do cases measured at the same time (and therefore under the same circumstances whatever they are) agree in their assessment of lymphoedema status.

The two methods will not agree on their actual scores as perometer measurements are in percentage differences and BEA measures are ratios. However we will assess the relationship between all the pairs of values using statistical techniques recommended by Bland and Altman for assessing agreement between methods of measurements with multiple observations per individual^{36,311} (see also analysis 3).

With 1100 cases consented to having measurements taken and followed-up, we would expect 231 to have developed lymphoedema (positive) using perometer assessment and 869 to be negative at 6 months. If we accept that BEA status has at least 95% sensitivity and 95% specificity against the perometer status then the 95% CI for sensitivity based on 231 cases is 91.42% to 97.49% and for specificity based on 869 cases is 93.31% to 96.47% (CI's calculated by 'exact' method). Consequently if sensitivity is <91 % or specificity is <93% we can conclude that the true BEA rates are not as high as 95%. This analysis can be done 6 months after the last case has their 6 months measurements taken. The perometer is deemed to be the gold standard.

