A further assessment of the BEA value cut off level will be made to see if a change in the standard definition is worth recommending (ROC analysis). This will be done at 18m from the start of the study (using cases accrued in the first year) and repeated on the new cases post 1 year recruitment to see if a new cut off level works on the second data group. The final sensitivity and specificity analysis will take place 6 months after the last case is recruited.

Analysis 2: Analysis of the sensitivity and specificity of the 18 month BEA assessment status (lymphoedema or not) against the 'gold standard' 18 month perometer assessment status (lymphoedema or not) using all data available at 18 months.

This analysis uses all the data available at 18 months, following the same logic and procedures as Analysis 1. Assuming at least 1,000 women are followed-up to 18 months after surgery, there will be more lymphoedema cases, this is estimated to be 35% of the total group (i.e. 350 cases). The sensitivity calculations produce a 95% CI for a 95% BEA sensitivity rate (333/350) against the perometer status at 18 months of 92.34 to 97.15 (again using the 'exact' method). The other 650 cases are used for the specificity calculation, here the 95% CI for 95% BEA specificity (618/650) has a 95% CI of 93.12 to 96.61. Consequently if sensitivity is <92% or specificity is <93% we can conclude that the true BEA rates are not as high as 95%.

Analysis 3: Assessment of the relationship between perometer measurement and BEA measurement. Any changes will be measured by both systems at different time points (1m, 3m, 6m, 12m and 18m and later on out to 5 years) and all results will be used as the modelling will be based on the paired perometer and BEA values. This will be used to define the relationship between the two methods (we will use Bland-Altman methods^{136,371} at individual time points and generalized estimating equations (GEE) regression models across time points). The relationship established may lead to a clearer definition of 'true' lymphoedema status when using either system.

Analysis 4: Cox regression multivariate analysis of the time to Lymphoedema (as defined by perometer) to find out what combination of variables gives the best prediction of these events.

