7 METHODS

Current methods of assessing arm volume include volume measurement using repeated tape measurement at predefined intervals along the limb, with the volume being calculated assuming a circular or elliptical truncated cone geometry. This method is tedious and time-consuming to perform. There is no standardisation of the number of circumferential measurements that are required to provide a reasonably accurate measurement of volume and it is thus not considered sufficiently validated to use in the study. Perometry volume determined from the 3D silhouette cast by the limb when passed through a ray of optoelectronic sensors¹⁴ is rapid, accurate and precise, but requires expensive equipment which is not very portable. The total volume of the arm may change for various reasons. The most common is weight gain but work or exercise induced muscle hypertrophy are cases in point where a simple total volume measurement is not immediately related to the parameter of interest i.e lymphatic volume. Additionally, there is dispute about the definition of lymphoedema. Many people have used the definition of greater than 10% arm volume increase compared to the contralateral arm, but others have claimed that a 200ml volume difference between the arms can be used to define unilateral lymphoedema following breast cancer^{11,11}. For the purposes of this study, we are using a greater than 10% arm volume increase measured by perometer on at least two occasions to identify women with lymphoedema secondary to axillary node clearance¹¹⁵¹ Czerniec et al found that perometer compared to bioimpedance spectrometry had a high concordance with bioimpedance $r=0.92$.

Perometer Measurement

The perometer is a standard arm volume measurement device that uses infra-red optoelectronic technology to detect and quantify limb changes. Perometer software then calculates the entire limb

volume and the % difference between the limbs and since a hard copy of each patient's data is retained on the database, it can be used to compare limb volume changes over time. Pre-surgical limb volume measurement accounts for pre-existing normal inter-limb variation which may range from 3-10% depending on arm dominance and activity level¹²⁹¹, hence the need for pre-surgical measurements. The upper limb volume and circumference are calculated by the perometer software (rather than the operator) and a comparison made between the previous reading from the same patient.

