The ratio of these values comparing the treated and untreated sides of these women with unilateral breast cancer (unaffected arm:affected arm) will be calculated. A patient will be classified as having lymphoedema when the impedance ratio is more than 3 standard deviations above normative data, with the normative data taking into account the significant effect of limb dominance.

- 1) Absolute BEA score (with a greater than 3sd level compared to the contralateral arm and reference leg equalling lymphoedema status);
- 2) Change in BEA score from baseline. Changes from preoperative baseline of >10% increase in BEA would represent a value score identifying lymphoedema using BEA.

All treatment decisions in the study will be based on Perometer measurements as this currently represents the standard of care internationally.

We will assess multi-frequency bioimpedance monitoring compared to perometer arm measurements in women after axillary node clearance (ANC) in 9 centres. We will use

bioimpedance monitoring during the study to determine its value in predicting response to compression garment therapy. Within the study we will assess reproducibility of both methods across centres and robustly establish both intra and interobserver error rates for both methods in the study population.

Please note, this assessment will only be carried out on the initial 1100 recruits, as part of the 5 year study. Subsequent recruits, as part of the 9 month study, will not undergo this as enough data will be gathered from the original cohort.

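### Bland-Altman agreement methods are planned on perometer and BEA readings in different units, with no conversion to a common scale

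*Protocol*

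**What the plan says.** All of the analysis text is in Protocol section 5.

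- **Purpose.** "Analyses 1 to 3 will assess whether BEA can be used instead of perometer in defining lymphoedema status".
- **Analysis 1 on scale.** "The two methods will not agree on their actual scores as perometer measurements are in percentage differences and BEA measures are ratios".
- **Analysis 1 on method.** The next sentence applies to all pairs of values the "statistical techniques recommended by Bland and Altman for assessing agreement between methods of measurements with multiple observations per individual".
- **Analysis 3.** Across visits, "all results will be used as the modelling will be based on the paired perometer and BEA values". To define the relationship, "we will use Bland-Altman methods" at individual time points, together with "generalized estimating equations (GEE) regression models across time points".

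Section 7 describes what each device gives. The perometer software returns "volume and the % difference between the limbs". For BEA the section takes "The ratio of these values comparing the treated and untreated sides", and it also names a change from the preoperative baseline with a 10% threshold. The form in Appendix A records a third quantity: the L-Dex score and its change from baseline.

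None of these places names a rescaling, calibration or standardisation before the two methods are compared by Bland-Altman methods.

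**The concern.** Limits of agreement are the mean of the paired differences plus or minus 1.96 times their SD. They can be read only if both methods estimate the same quantity in the same unit. Here one reading is a percent volume difference and the other an impedance ratio or a device score. Their difference has no unit, and its spread mixes the relation between the methods with their arbitrary scales.

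The protocol sees the mismatch and still names an agreement method, so this is a method badly fixed and not a detail left out. At stake is the agreement part of secondary endpoint 1, the comparison of BEA with the perometer. A reader could take the reported limits as evidence for or against replacing one device with the other, when they mostly reflect the choice of units.

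**Working it through.** The protocol gives no limits of agreement, so there is no figure to reproduce. The check asks how limits on unconverted readings would behave as the correlation r between the methods changes.

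**Inputs**

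- Perometer SD, s1. Section 5 expects about 33% of women below 4% increase and 46% between 4% and 10%. Section 2.0 expects 21% above 10%. One normal curve through these points gives s1 = (10 − 4) / (0.440 + 0.806) = 4.81 points. A rounder value of 5 is used as an alternative.
- Correlation: 0.93 in section 5 (0.92 in sections 1.4 and 7).
- BEA SD, s2: not in the documents. Assumed 0.02 to 0.10 for the ratio and 8 to 10 for L-Dex.

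**Formulas**

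- Unconverted half-width = 1.96 × √(s1² + s2² − 2·r·s1·s2)
- Half-width after linear calibration of BEA to the perometer scale = 1.96 × s1 × √(1 − r²)

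**Raw ratio, s1 = 4.81 (unrounded 4.814)**

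| s2 | r = 0 | r = 1 |
|---|---|---|
| 0.02 | ±9.44 | ±9.40 |
| 0.05 | ±9.44 | ±9.34 |
| 0.10 | ±9.44 | ±9.24 |

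The perometer's own spread is 1.96 × 4.814 = ±9.44, so the limits show little else. The alternative s1 = 5 with s2 = 0.05 gives ±9.80 at r = 0 and ±9.70 at r = 1, the same pattern.

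**L-Dex, s1 = 5**

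| s2 | r = 0 | r = 0.93 | r = 1 |
|---|---|---|---|
| 8 | ±18.5 | ±7.5 | ±5.9 |
| 10 | ±21.9 | ±11.1 | ±9.8 |

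At r = 1 the half-width is 1.96 × |5 − s2|: 1.96 × 3 = 5.9 and 1.96 × 5 = 9.8. It is not zero even when BEA predicts arm volume without error.

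**After calibration**

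| s1 | r = 0 | r = 0.80 | r = 0.93 | r = 1 |
|---|---|---|---|---|
| 4.81 | ±9.4 | ±5.7 | ±3.5 | 0 |
| 5 | ±9.8 | ±5.9 | ±3.6 | 0 |

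Set the last two tables side by side for s1 = 5. A perfect linear relation seen through L-Dex with SD 10 gives ±9.8, the width that calibrated limits give when the methods are unrelated. With SD 8 it gives ±5.9, the calibrated width at r = 0.80.

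**The case against.** The strongest reply is that the authors knew of the unit problem and aimed at a relationship, not at equality of scores. Neither analysis mentions subtraction or limits of agreement, and an analysis plan that is not shown may set the scaling. This stands in part: a reader might infer that subtracting raw readings is prescribed, and the protocol does not say so. But the techniques it names are described there as techniques for agreement, they are applied to the paired values, and no conversion is given. Followed as written, the text leads to differences between unlike units.

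A second reply is that the result depends on the BEA metric, and this stands too. A reader of the raw-ratio table might infer that the limits carry no information at any correlation. That holds for the ratio only; for L-Dex the limits narrow clearly as r rises. If BEA were expressed in percent with an assumed SD of 5 against 4.81, they would run from ±13.6 at r = 0 to ±0.4 at r = 1. That near-zero value comes from assuming almost equal SDs. A percent change in impedance is still not a percent change in volume, so calibration is still needed.

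A third reply is that little hangs on the output, and this is right as to reach. Sensitivity and specificity at 6 and 18 months, the ROC work and GEE regression also serve the comparison, and no decision rule uses the Bland-Altman result. The planned regression could even supply a residual spread, but the protocol does not link it to the agreement analysis.

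Finally, the SD of 4.81 is rough. The three groups are cumulative up to 6 months, and the fit implies a mean of 4 + 0.440 × 4.81 = 6.1%, against the 5.14% quoted in section 7 for 6 months.

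**Conclusion.** The point holds for the agreement component of Analyses 1 and 3 and no further. Limits of agreement on unconverted readings would not measure agreement. On the raw ratio they are about ±9.2 to ±9.4 points at any correlation. On L-Dex they vary with correlation but remain about ±6 to ±10 under a perfect linear relation.

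The BEA SDs are assumptions and the perometer SD is approximate, so the widths are illustrations. The direction is firmer. The ratio result needs only that the ratio's SD is small beside the perometer's SD in points. The L-Dex result needs only that the two SDs differ.

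A reader might infer that the whole of secondary endpoint 1 depends on this output. The documents do not support that, because the classification, ROC and regression analyses stand without it. The change should still be made: the method is named in the protocol, serves a stated secondary endpoint and is cheap to correct.

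**What to change.** Amend Analyses 1 and 3 in section 5 as follows.

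1. State which BEA metric is used: impedance ratio, change from baseline, or L-Dex.
2. Calibrate that metric to percent arm-volume change, for example in the cases accrued in the first year, which Analysis 1 already uses to develop the ROC cut-off.
3. Convert BEA to predicted percent arm-volume change and report limits of agreement only on that scale, in the later cases, so that calibration and assessment use different women.
4. Drop limits of agreement on unconverted readings.

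The cost is a change of wording, a small amount of extra programming, and somewhat fewer cases for the limits because the first-year cases are used for calibration. No new data are needed, and the sensitivity, specificity, ROC and GEE analyses stay as they are.

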4.3 Secondary Objectives

- 1) Comparison of multi-frequency BEA with perometer measurement.
- 2) Prediction of lymphoedema by multi-frequency BEA at 24 months.
- 3) Quality of life in each group (T01 and FACT B+4).
- 4) Multivariate model assessment of factors predicting lymphoedema at 24 months.
- 5) Lymphoedema symptoms related to changes in arm volume and bioimpedance readings.

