For this 'modelling' analysis we will use 'time to the first lymphoedema event per case' as the measure (cases not becoming lymphoedema will be censored at their last assessment time) and apply a Cox regression multivariate analysis to see what variables (if any) predict the long term outcome. The variables listed below are candidates. Concerns about the treatment paradox affecting this analysis will be dealt with by excluding cases who develop lymphoedema before 6 months and using a factor 'sleeve' v 'no sleeve' in the model to adjust for the cases treated in PLACE.

BMI, dominant limb, postoperative radiotherapy, previous sentinel node biopsy, cigarette smoking, weight gain, and age. As we will be measuring the patient's assessment of their own status using FACT-B and the Lymphoedema Symptom Checklist we will also use individual question responses and the overall scores for these questionnaires out to 6 months. The BEA values and perometer values are available at baseline, 3 months and 6 months. The 3 months and 6 months values will be used as distinct time points or as summary scores over the 3 measurements. It may well be possible to have a factor that represents 'early treatment' or 'lymphoedema status before 6 months', in which case all the information will be used. These variables will be assessed univariately and then as part of a multivariate model to see if any predict lymphoedema status by 18 months follow up.

As routine clinical data on lymphoedema status will be available in due course with 5 year follow up, a subsequent analysis will be possible to build a predictive model of outcomes up to 5 years.

This analysis will take place 18 months after the last case is entered. For the multivariate regression analyses, it is typically recommended that between 10 and 30 cases per variable are used. The higher number of cases per variable are required when the relationships are weaker. With approximately 1000 cases this should allow us to examine around 30 variables with at least sufficient power to pick up moderately weak relationships. See analysis 4 for the type of variables we will be assessing.

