All percentages for the 3 groups (A-C) are estimated from ALMANAC Trial data (see Annex 4d). None of the analyses outlined will use cases where a treatment for lymphoedema has been given prior to 6 months as explained above. A "treatment paradox" will not affect analyses 1 to 3 and treatment will be a variable in analysis. Potentially, the predictive value of a measurement at 6 months by perometry of the arm may be altered by treatment when assessing lymphoedema at 18 or 36 months. We do not believe this will occur for the majority of patients but in any case we will take account of this in the Cox multivariate regression analysis based on perometer measurements at 18 and 36 months and by looking at variables which include treatment with a compression sleeve. As we indicated in the flow diagram of this study, 3 possibilities may arise:

- Group A: Women in whom the arm volume increase is less than 4% at all time points up to 6 months (approximately 33% of the population; 330 individuals). None of these patients will undergo treatment within the first 6 months and therefore the measurement at 6 months will not be subject to "treatment paradox" and should they subsequently develop lymphoedema before 18 months, they will be registered as having developed the lymphoedema event in a time-dependant manner for the multivariate analysis and subsequent treatment will not affect this analysis.
- Group B: Women who will have developed a 4-10% arm volume increase by 6 months (estimated as 46% of the total group; 460 patients). Around 135 women from this group (with a 4-8.9% volume increase) will go into the PLACE trial and have a sleeve applied and a similar number will go into the PLACE trial and will not have an arm sleeve applied.

Thus, in this group there will be 325 patients (460 minus 135) who are not treated until they develop lymphoedema and will not have a "treatment paradox" for the same reason as previously described. Out of the 135 cases allocated to the sleeve arm within the PLACE trial, who are chosen at random, we will use their data in a multivariate analysis as we will incorporate it as a factor, sleeve versus no sleeve in building the model.

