- Group C: Women who develop greater than 10% arm swelling by 6 months (approximately 210 patients). Arm swelling of greater than 10% at 1 month will need confirmation but in current practice, we would review these patients at 3 months, before deciding to put on an arm sleeve as some women do observe amelioration of swelling over this period following the operation. Thus we will have 3 month perometer readings on all patients in this group to compare with 3 month BEA measurements. All other patients will provide 6 month perometer and BEA measurements and will therefore be eligible for the analysis of the prediction of arm swelling at 18 and 36 months. The data for patients who have undergone treatment before 6 months in this group will not be included in our multivariate analysis, although we expect few cases to be excluded in this way.

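### Analysis 4 excludes women with lymphoedema before 6 months from a model of time to lymphoedema, under rules that conflict within section 5, and could lose up to 60% of the events expected by 18 months

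*Protocol*

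**What the plan says.** Secondary objective 4 (section 4.3) is: "Multivariate model assessment of factors predicting lymphoedema at 24 months". Analysis 4 (section 5) addresses it with a Cox model of time to first lymphoedema by perometer. The candidate predictors mix factors known at surgery (BMI, dominant limb, age, smoking, previous sentinel node biopsy) with later ones (radiotherapy, weight gain, and the 3- and 6-month perometer, BEA and questionnaire values).

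Section 5 treats early cases in four ways:

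- **Analysis 4, main rule:** "Concerns about the treatment paradox affecting this analysis will be dealt with by excluding cases who develop lymphoedema before 6 months". A sleeve factor adjusts for women treated in PLACE.
- **Analysis 4, alternative:** "It may well be possible to have a factor that represents 'early treatment' or 'lymphoedema status before 6 months', in which case all the information" would be used.
- **Paragraph introducing Groups A to C:** none of the analyses uses women treated for lymphoedema before 6 months. Analysis 1, however, expressly accepts treated women.
- **Group C paragraph:** "The data for patients who have undergone treatment before 6 months in this group will not be included in our multivariate analysis", and then "although we expect few cases to be excluded in this way".

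For Group A, the same section says that women who later develop lymphoedema are kept (the last word of the quote refers to the multivariate model): "they will be registered as having developed the lymphoedema event in a time-dependant manner for the multivariate analysis and subsequent treatment will not affect this". The untreated women of Group B are kept for the same reason.

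**The concern.** The main rule removes women because they had the event being modelled. For a predictor fixed at surgery there is no need for this. Outside PLACE, section 3.4 starts treatment on a confirmed increase above 10%, so treatment follows the event and cannot move its date. That is the protocol's own argument for keeping Groups A and B, and it applies equally to Group C women whose treatment followed the event.

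The alternative does not repair this. In a model of time to first lymphoedema, a covariate recording lymphoedema before 6 months is the outcome entered as a predictor. A covariate for early treatment outside PLACE comes close to the same thing, because the event triggers the treatment.

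Three things are at stake:

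- which women and events the model contains, since the written rules select different sets;
- the meaning of the result, since after the exclusion it applies only to women still free of lymphoedema at 6 months;
- whether the data can carry about 30 candidate variables.

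**Working it through.** **Inputs, all from the protocol**

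- Lymphoedema by 6 months: "we would expect 231 to have developed lymphoedema (positive) using perometer assessment and 869 to be negative at 6 months" (Analysis 1, on 1100 women). Group C is put at about 210.
- Lymphoedema by 18 months: 35%, or 350 of 1000 (Analysis 2).
- Groups A, B and C: 330, 460 and 210.
- Women with a 10% increase at 3 or 6 months: 5% (section 1.4).
- Planned model: about 30 variables on about 1000 cases, with 10 to 30 cases per variable recommended (Analysis 4).

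**Step 1. Reproduce the plan's figures.** 0.21 × 1100 = 231. 0.21 × 1000 = 210. 0.35 × 1000 = 350. 330 + 460 + 210 = 1000. The exact 95% interval for 333/350 is 92.34% to 97.15%, as stated in Analysis 2. The figures agree once a single base is used; I use 1000 below.

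**Step 2. Share of events removed** = early events / events by 18 months.

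- All of Group C: 210/350 = 60.0%. On the 1100 base, 231/(0.35 × 1100) = 231/385 = 60.0%.
- The 5% rate in section 1.4: 50/350 = 14.3%.

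The protocol does not say how many of Group C arise before the 6-month visit and how many are first found at it. If the fraction arising earlier is assumed to be 25%, 50% or 75%, the share is 15%, 30% or 45%.

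**Step 3. Events per variable** = remaining events / 30.

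| Early events removed | Events left by 18 months | Events per variable |
|---|---|---|
| None | 350 | 11.7 |
| 50 (5% rate) | 300 | 10.0 |
| 105 (half of Group C, assumed) | 245 | 8.2 |
| 210 (all of Group C) | 140 | 4.7 |

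The protocol's rule counts women: 1000/30 = 33 per variable, and 790/30 = 26 even without Group C. The information in a Cox model comes from events. Read as events, the 10-to-30 guide is just met with all 350 and is missed by half with 140.

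**Step 4. Precision.** My assumptions are a balanced binary factor, two-sided 5% and 80% power. The detectable hazard ratio is exp[(1.96 + 0.84)/√(0.25 × events)]:

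- 350 events: exp(2.80/9.35) = 1.35
- 140 events: exp(2.80/5.92) = 1.61

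**Step 5. Population described.** If all of Group C is out, the 18-month risk among those left is 140/790 = 17.7%, against 35% in the cohort. The 17.7% is a correct conditional risk, but it is not the risk facing a woman at surgery.

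**The case against.** **The exclusion is a landmark analysis in all but name.** Section 5 also sets the aim of using information from the operation and the first 6 months to predict status at or beyond 18 months. For 3- and 6-month predictors, starting with women free of lymphoedema at 6 months is legitimate. The stated worry, that treatment may alter the 6-month reading as a predictor, is genuine for a woman given a sleeve at 3 months. This stands. A reader might infer that the analysis cannot serve objective 4 at all, and the documents do not support that. What is left is that the landmark is not declared and that the same exclusion is applied to predictors that do not need it.

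**60% is a ceiling.** The rule says before 6 months, while the 210 counts women by 6 months. This stands too. A reader might take 60% as the expected loss, but the protocol does not give the number needed to say so.

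**The expectation of few exclusions is not disproved.** A reader might set few against 210 and call it wrong. That sentence covers only Group C women treated before 6 months, whose number is not stated. It is doubtful, because section 2.0 has sleeves applied to women above 10% at 3 months, and it does not carry over to the wider rule in Analysis 4. No count can replace it from the documents.

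**The economic model need not be affected.** A reader might infer that understated risks pass into the cost-effectiveness work. Section 2.0 introduces the prediction model used there directly after a multiple logistic regression for which no such exclusion is stated, so that inference is conjecture. So is any claim that the hazard ratios themselves are biased by the exclusion, which depends on unmeasured differences in susceptibility whose size the documents do not give.

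**Conclusion.** The point holds in this form. Section 5 gives incompatible rules for early cases in Analysis 4. The main rule discards outcome events without need for predictors known at surgery, and the alternative would enter the outcome as a predictor. The loss is at most 60% of the events expected by 18 months (210 of 350) and 14% on the section 1.4 rate. Events per variable for 30 variables fall from 11.7 to between 10.0 and 4.7, which undercuts the statement that about 1000 cases support around 30 variables.

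These sizes rest on the protocol's 21%, 35% and 5% rates, the last of which does not sit easily with the first, and on events up to 18 months. No event count is given for the 24 months named in the objective, and longer follow-up would add events. The matter concerns a secondary objective; the primary incidence endpoint is not affected.

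**What to change.** Replace the differing statements in section 5 with one rule and two models.

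1. **All-events model.** Cox regression from surgery in all women of the five-year study, counting every first lymphoedema event including those before 6 months, with baseline and operative predictors only. Keep the planned sleeve adjustment for PLACE, switched on from the date the sleeve is applied. Any absolute risk quoted for the whole cohort should come from this model.
2. **Landmark model.** Women free of lymphoedema at 6 months, clock starting at 6 months, adding the 3- and 6-month perometer, BEA and questionnaire values. Report it as conditional on being free at 6 months, and say how women first found positive at the 6-month visit are classed.

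Delete the option of a covariate for early lymphoedema status. State the expected number of exclusions under the chosen rule, and set the number of variables by events. With the protocol's 10-to-30 guide read as events, 350 events support about 11 to 35 variables in the first model (350/30 to 350/10). If all of Group C is out of the landmark set, 140 events support about 4 to 14 in the second (140/30 to 140/10), before events after 18 months are added.

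The cost is a change of wording and one further Cox model on data already collected. No patients or visits are added. Two models are reported instead of one.
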